	 Any serious medical condition or abnormality of clinical laboratory tests that, in the investigator's judgment, precludes the patient's safe participation in and completion of the study In the opinion of the investigator, progression to death is imminent and highly likely within the next 24 hours, irrespective of the provision of treatments Current participation in any other interventional investigational trials
Study treatment	 Arm 1: Mavrilimumab 6 mg/kg IV infused over approximately 1 hour Arm 2: Matching placebo infused over approximately 1 hour Mavrilimumab or placebo infusions will be prepared and blinded by an unblinded pharmacist or designated staff member. Patients will be randomized according to their age (<50; 50-69; ≥ 70 yo), and their respiratory stratum (PaO₂/FiO₂ 200-300 or 100-199 mmHg) at randomization.
Treatment of interest	Randomized mavrilimumab or placebo as described above. In addition, all patients will receive standard of care per local practice for the treatment of COVID-19-induced pneumonia. The SOC may include but not be limited to anti-viral treatment, low-dose corticosteroids (≤ 15 mg of prednisone or equivalent) and/or hydroxychloroquine or chloroquine and/or supportive care.
Rescue treatment	In worsening patients, treatment with investigational COVID-19 treatments, such as but not limited to antimicrobials, interferon beta, or convalescent serum, is permitted, if approved by the Promoter. Particular attention should be taken when considering rescue treatment with biologic or targeted-synthetic DMARDs/immuno-suppressors due to the risk of potential severe immune-suppression if given in combination with the investigational drug. Systemic corticosteroids (low- or high-dose per medical judgement) could also be used as a rescue medication.
Efficacy assessments	The WHO-adopted 7-point ordinal scale of clinical status will be assessed on a daily basis at baseline and after study treatment during hospitalization as well as at day 7, 14, and 28. NEWS2 score will be assessed on a daily basis at baseline and after study treatment during hospitalization day 7, 14, and 28.

Safety assessments	Adverse event monitoring, physical examinations, and monitoring
	of laboratory safety values.
Other assessments	Standard safety and laboratory assessment (hematology and
	clinical chemistry) will be performed during hospital stay and
	outpatient visits after discharge from hospital (See Schedule of

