Eligible patients will have biomarker sampling according to the Assessment and Procedures Schedule (see below). Additional safety assessments will be performed approximately as described in the Assessment and Procedures Schedule. Additional follow-up visits will occur on Days 7, 14, 28, 56 and 84 either by phone if previously discharged or in the hospital if still hospitalized. If a patient is hospitalized for longer than Day 28, all invasive protocol assessments will be discontinued except at week 8 and 12, if still hospitalized. If the patient has been discharged, then patients should be phoned for follow-up and data collected as in the Assessment and Procedures Schedule. In addition, unscheduled visits are permitted at or after discharge, as needed.

Deaths and SAEs will be monitored in real time with routine pharmacovigilance and by an external, independent DSMB in order to detect any unexpected safety signal. The DSMB will function independently of all other individuals associated with the conduct of this clinical trial. Patients who do not meet the criteria for participation in this study (screen failures) may not be re-screened.

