4.2 Rationale for mavrilimumab dose and administration route

In a Phase 1 single-ascending-dose (SAD) study the pharmacokinetics (PK) of mavrilimumab were tested at doses of 0.01-10 mg/kg in patients with mild-to-moderate RA. Mavrilimumab was well tolerated in a single IV injection up to 10 mg/kg in subjects with mild to moderate RA at all dose levels. (Burmester 2011). Pharmacokinetic and pharmacodynamic simulations from studies in subjects with RA coupled with the PK data from the Phase 1 study, indicate that a single dose of ≥ 3 mg/kg will provide EC90 (the concentration that leads to 90% maximal response) for the RA endpoint ACR50 (American College of Rheumatology 50% response criteria; data on file) for up to 22 days. Therefore, at doses ≥ 3 mg/kg, the pharmacologic profiles indicated sustained peripheral inhibition of the GM-CSF-R α signaling axis for at least three weeks.

In preclinical studies, the potential systemic effects of mavrilimumab (CAM-3001) have been investigated in a 4-week and an 11-week repeat dose cynomolgus monkey study. There were no effects attributable to administration of CAM-3001 (mavrilimumab) in doses up to 100 mg/kg/week for 4 weeks in a study conducted in accordance with Good Laboratory Practice (GLP). In an 11-week exploratory (non-GLP) study there were no effects attributable to IV administration of CAM-3001 (mavrilimumab) following 10 mg/kg/week, and the no observed adverse event level (NOAEL) was 100 mg/kg/week. An immunocytochemistry screen to test in vitro binding of mavrilimumab to a panel of normal human tissues revealed no non-specific or unanticipated binding of the antibody.

Reference for further details on safety studies in animals and humans is made to the Investigator's brochure.

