for biomarkers will not be conducted (but collected if performed for other indications). If the patient remains hospitalized, however, all assessments noted in the table should be conducted on the visit day noted. * If patient is discharged prior to Day 28, then all assessments listed for Day 28 should be conducted on the day of discharge. Visits at Days 14, 28, 56, 84 should be conducted via phone for patients who were discharged prior to the visit. These phone visits should only collect Clinical status evaluation with 7-point

⁽¹⁾ Results confirming positive SARS-CoV-2 virus by PCR or by other approved diagnostic methodology available within one week;

chest x-ray or CT scan within 4 days prior to randomization may be used for eligibility; ECG in the previous 2 weeks

(2) All assessment at day 0 must be conducted prior to mavrilimumab dosing

(3) Blood cultures are acceptable if taken in the 24 hrs before randomization. At day 0 must be they must be taken prior to mavrilimumab dosing

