Adverse events of hepatic function abnormality of special interest are defined as any increase in ALT or AST to greater than $3 \times ULN$ and concurrent increase in bilirubin to greater than $2 \times ULN$. Concurrent findings are those that derive from a single blood draw or from separate blood draws taken within 8 days of each other. In the event of hepatic function abnormality where the etiology is unknown, timely follow-up investigations and inquiries should be initiated by the investigational site, based on medical judgment, to make an informed decision regarding the etiology of the event. Investigational product will not be administered to any subject reporting ALT or AST to greater than $3 \times ULN$ and concurrent increase in bilirubin to greater than $2 \times ULN$

Acute and Delayed Hypersensitivity Reactions

Biologic therapies are known to be associated with an increased risk of immediate and delayed hypersensitivity reactions as well as anaphylaxis. Anaphylaxis and severe hypersensitivity reactions are required to be reported within 24 hours of knowledge of the event, and ADA samples should be collected as possible.

Clinically Significant Pulmonary Abnormality

Any subject who develops new clinically significant pulmonary symptoms or signs should be referred to a qualified specialist for further specific assessment. Symptoms and signs triggering such referral include but are not limited to an increase in shortness of breath or difficulty breathing, exacerbation of current respiratory symptoms, or a significant

deterioration in dyspnea score. Subjects who are referred for evaluation by a specialist will undergo a diagnostic evaluation to determine the nature and origin of the pulmonary symptom(s)/sign(s) and to determine if PAP may be present. At the discretion of the investigator or specialist additional tests may be required such as a repeat chest x-ray, and/or a chest high resolution computed tomography scan, full PFTs including DLCO measurement, bronchoscopy with bronchoalveolar lavage, and cytological and/or ultrastructural evaluation of the cells recovered by lavage to identify findings consistent with a diagnosis of PAP. Any subject who has been referred for a specialist pulmonary evaluation may be instructed to stop the investigational product until the symptom(s) or sign(s) causing the referral have resolved.

Neutropenia

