Adverse events of neutropenia of special interest are defined as an ANC < 1.0×109 cells/L. Investigational product will not be administered to any subject who has an ANC < 1.0×109 cells/L. Administration of investigational product may continue in the event that the ANC > 1.5×109 cells/L and following agreement with the medical monitor.

Serious Infection

Grade 3 severity infections that require treatment with IV therapy (antibiotics, antiviral, or antifungal) and opportunistic infections will be considered serious even if they do not require in-patient hospitalization. Every effort should be made to identify the causative pathogen through prompt and appropriate investigation by the investigator or reporting physician.

Pregnancy reporting

Women should use effective contraceptives during treatment with mavrilimumab and for up to 3 months after dosing.

If a female trial participant becomes pregnant, the study should be stopped, and the trial participant must be asked to read and sign pregnancy consent form to allow the Study Doctor ask about her pregnancy. To ensure participant safety, each pregnancy occurring after signing the informed consent must be reported to the Promoter within 24 hours of learning of its occurrence. The pregnancy should be followed up to determine outcome, including spontaneous or voluntary termination, details of the birth, and the presence or absence of any birth defects, congenital abnormalities, or maternal and/or newborn complications.

Pregnancy should be recorded and reported by the investigator to CMO & PS. Pregnancy follow-up should be recorded on the same form and should include an assessment of the possible relationship to the study treatment any pregnancy outcome. Any SAE experienced during pregnancy must be reported.

Reporting of study treatment errors including misuse/abuse

Medication errors are unintentional errors in the prescribing, dispensing, administration or monitoring of a medicine while under the control of a healthcare professional, participant or consumer (EMA definition).

Misuse refers to situations where the medicinal product is intentionally and inappropriately used not in accordance with the protocol.

Abuse corresponds to the persistent or sporadic, intentional excessive use of a medicinal product, which is accompanied by harmful physical or psychological effects.

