11.1 Determination of sample size

The sample size estimation for this study is based on the primary efficacy endpoint, time to the absence of need for oxygen supplementation. When use a two-side alpha value of 0.05 and assume the proportions of patients who do not need oxygen supplementation by day 14 are 83% and 40% for mavrilimumab and placebo arms respectively, total 28 events are required to achieve a 90% power using a log-rank test.

Approximately total 50 patients will be randomized with a 1:1 ratio to obtain the total target number of events. Analysis for treatment effect will be based on the evaluable population which includes all subjects who are randomized and receive KPL-301/placebo treatment.

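### Post-discharge laboratory work is stated inconsistently, and as Table 1 reads, the window for finding two blood-test-only AESIs depends on how soon the patient recovers

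*Protocol*

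**What the plan says.** Four places describe laboratory work after discharge, and they do not agree.

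- **Synopsis, Other assessments.** Haematology and clinical chemistry are performed during the hospital stay and at "outpatient visits after discharge from hospital (See Schedule of" Assessments table.
- **Section 4, Study design.** Visits on Days 7, 14, 28, 56 and 84 take place "either by phone if previously discharged or in the hospital if still hospitalized".
- **Section 8.1, Table 1.** Haematology and chemistry are taken on alternate days up to discharge, and on Days 7, 14 and 28. In the two follow-up columns they are entered only where a result exists.
- **Section 8.1, footnote to Table 1.** "Visits at Days 14, 28, 56, 84 should be conducted via phone for patients who were discharged prior to the visit". Day 7 is not in this list. A patient who leaves before Day 28 has the Day 28 assessments on the day of discharge.

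Two adverse events of special interest in section 10.1 have laboratory definitions:

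- "Adverse events of neutropenia of special interest are defined as an ANC" below 1.0 × 10⁹/L.
- "Adverse events of hepatic function abnormality of special interest are defined as any increase in ALT or AST to greater than" 3 × ULN, with bilirubin above 2 × ULN.

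Section 3.2 makes AESIs and clinically significant laboratory changes a safety endpoint, and section 10.1 continues adverse event monitoring to the end-of-study visit. On duration of action, section 4.2 states that doses of 3 mg/kg or more "indicated sustained peripheral inhibition of the GM-CSF-R α signaling axis for at least three weeks". The trial gives a single dose of 6 mg/kg.

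**The concern.** A site cannot follow both the synopsis and Table 1. If it follows Table 1, the last required blood sample falls at or soon after discharge. A patient can then still be under drug action, by the protocol's own account, with no further required test for the two AESIs that only a test can show. A sample taken on an early day of discharge would also stand in the data as Day 28.

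Patients generally leave hospital after they come off oxygen, which is the primary endpoint. The time during which a laboratory AESI can be found is therefore set by the efficacy outcome. If mavrilimumab shortens the need for oxygen, its patients are tested for less time, and a crude comparison of the numbers with neutropenia or liver abnormality leans towards the drug.

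**Working it through.** **1. The protocol's own figure.** Section 11.1 reads "When use a two-side alpha value of 0.05" and takes day-14 proportions off oxygen of "83% and 40% for mavrilimumab and placebo arms respectively". With exponential times:

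- λ = −ln(1 − 0.83)/14 = 0.1266 per day (mavrilimumab)
- λ = −ln(1 − 0.40)/14 = 0.0365 per day (placebo)
- Hazard ratio = 0.1266/0.0365 = 3.47
- Schoenfeld events = 4 × (1.960 + 1.282)² / (ln 3.47)² = 27.2, rounded up to 28

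This matches the stated 28 events, so the exponential model agrees with the sample-size calculation. That calculation is not in dispute; its rates serve only to gauge the size of the problem.

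**2. Days under required laboratory observation in the first 28.** Assume discharge occurs L days after coming off oxygen, required draws end at discharge, and deaths are ignored. The mean is L + [1 − exp(−λ(28 − L))]/λ.

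| Lag L | Mavrilimumab | Placebo | Placebo/mavrilimumab |
|---|---|---|---|
| 5 days | 5 + (1 − 0.054)/0.1266 = 12.5 | 5 + (1 − 0.432)/0.0365 = 20.6 | 1.65 |
| 3 days | 3 + (1 − 0.042)/0.1266 = 10.6 | 3 + (1 − 0.402)/0.0365 = 19.4 | 1.8 |
| 0 days | (1 − 0.029)/0.1266 = 7.7 | (1 − 0.360)/0.0365 = 17.5 | 2.3 |

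**3. If Day 7 is drawn in everyone.** This is the reading the footnote allows. Count the first 7 days as covered for all patients, with no lag. The mean is 7 + [exp(−7λ) − exp(−28λ)]/λ:

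- Mavrilimumab: 7 + (0.412 − 0.029)/0.1266 = 10.0
- Placebo: 7 + (0.775 − 0.360)/0.0365 = 18.4
- Ratio 1.8, inside the range above

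**4. What this could do to a crude comparison.** This is an illustration by simulation, with 400,000 patients per arm. Draws are on alternate days plus Day 7 while in hospital, and once at discharge. A laboratory abnormality lasting 5 or 10 days is equally frequent in both arms, with onset uniform over 22 days, the longest duration of effect in section 4.2.

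- No lag: about 34% vs 69% of abnormalities caught, giving an apparent risk ratio of 0.49.
- 5-day lag: about 54% vs 80% caught, giving an apparent risk ratio of 0.68.

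The true ratio is 1.0 in both cases. Mean scheduled draws through Day 28 are 4.8 vs 9.9 with no lag, and 7.5 vs 11.5 with a 5-day lag.

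**The case against.** A reader might infer that laboratory monitoring stops altogether at discharge. The protocol does not say that. Results that exist are recorded in the follow-up columns, section 4 allows unscheduled visits, adverse events are collected to the end of study, and section 8.5 follows abnormalities already found until they resolve. What appears to end is the required draws. Results obtained for other reasons are likely to be sparse and prompted by symptoms, and following a known abnormality does not find a new one.

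The footnote does not put Day 7 on its phone list, so a patient discharged before then may still be due a Day 7 sample. That is correct. It is part of the contradiction with section 4, and it reduces the imbalance without removing it. The footnote is also incomplete in the copy at hand. The surviving fragment on later sampling names biomarkers, so the point does not rest on it for safety haematology and chemistry.

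The zero-lag case is an extreme. The ordinal scale has a category for patients in hospital without oxygen, and the primary endpoint needs a 24-hour period, so some lag is expected. The lagged rows are the more realistic ones.

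A further tempting inference is that a true 1.65- to 2.3-fold excess of laboratory AESIs would be hidden. That needs a hazard constant over 28 days, which the documents do not support. Events soon after dosing would be sampled in both arms.

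Finally, section 11.2 speaks of an incidence rate, which could mean person-time; safety is descriptive; and denominators can be set in the SAP, which is not shown. This answers a complaint about missing analysis detail. It does not settle which visit schedule applies, and no analysis recovers samples that were not taken.

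**Conclusion.** The point holds as an inconsistency with a consequence for the safety comparison. The synopsis, section 4 and Table 1 with its footnote do not give one post-discharge laboratory schedule. As Table 1 reads, required draws appear to end at or soon after discharge, so the window for two laboratory-defined AESIs depends on recovery.

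If the drug works as assumed, placebo patients have 1.65 to 2.3 times as many days under required laboratory observation in the first 28, and crude incidence would tend to favour mavrilimumab. This rests on the 83% vs 40% planning rates, exponential times, an assumed lag of 0 to 5 days and no deaths. The distortion of any AESI comparison also depends on when events occur. The three-week duration of action comes from rheumatoid arthritis data, not COVID-19. If the arms recover at the same rate, the imbalance disappears, but the early end of required sampling remains. The primary analysis and the 28-event calculation are unaffected.

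**What to change.** - Reconcile the synopsis, section 4, and Table 1 with its footnote, including the status of Day 7, so that a single post-discharge laboratory schedule applies. Which schedule is for the sponsor to decide.
- Record the sample taken on leaving hospital as a discharge sample with its actual study day, not as Day 28.
- If follow-up stays by phone only, report laboratory-defined AESIs and laboratory shifts per patient-day under laboratory observation, give the number of samples per arm, and limit the laboratory safety conclusion to the in-hospital period.

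The cost is a wording amendment, a label in the eCRF, slightly more analysis and a narrower safety statement. The person-time rate removes only part of the bias, because patients who are still being sampled are the sicker ones. That is why the limit on the conclusion is needed as well.

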8.2 Screening / screening failures

No rescreening will be permitted. Participants who sign an informed consent form and subsequently found to be ineligible prior to randomization will be considered a screen failure. The reason for screen failure should be recorded on the appropriate CRF. The demographic information, informed consent, and Inclusion/Exclusion pages must also be completed for screen failure participants. No other data will be entered into the clinical database for participants who are screen failures, unless the participant experienced a serious adverse event during the screening phase.

If the participant fails to be randomized, the IRT must be notified within 2 days of the screen fail that the participant was not randomized.

Participants who are randomized and fail to start treatment, e.g. participants randomized in error, will be considered an early terminator. The reason for early termination should be recorded on the appropriate CRF.

8.3 Participant demographics/other baseline characteristics

Participant race and ethnicity are collected and analyzed to identify variations in safety or efficacy due to these factors as well as to assess the diversity of the study population as required by Health Authorities.

8.4 Efficacy

Clinical status (7-point ordinal scale)

Assessment of clinical status using a 7-category ordinal scale (WHO 2020) will be recorded at baseline and then again once daily through Day 28 of the Study Period if hospitalized (Appendix 1). If a patient is discharged from the hospital, the assessment will be made by phone on the visit dates noted in Table 1. Each day, the worse score for the previous day will be recorded. (i.e. on Day 5, Day 4 score is obtained and recorded as Day 4. The scale is as follows:

- 1. Not hospitalized, no limitations on activities
- 2. Not hospitalized, limitation on activities
- 3. Hospitalized, not requiring supplemental oxygen
- 4. Hospitalized, requiring supplemental oxygen
- 5. Hospitalized, on non-invasive ventilation or high flow oxygen device
- 6. Hospitalized, on invasive mechanical ventilation or ECMO
- 7. Death

Vital signs and oxygen saturation

Vital sign measurements include respiratory rate, pulse rate, systolic and diastolic blood pressure, and body temperature. Peripheral oxygen saturation should also be measured at the same time as the vitals. For patients requiring supplemental oxygen, the oxygen flow rate (L/min) and/or fraction of inspired oxygen (FiO2) should be recorded.

CONFIDENTIAL

In order to allow assessment of the NEWS2 score (Appendix 2), the vital sign parameters and oxygen saturation should be recorded together once per day, for the duration of the hospitalization during the study.

National Early Warning Score 2 (NEWS2)

In addition to the vital signs, the patient's level of consciousness and the presence/absence of respiratory support must be recorded. The NEWS2 parameter for respiratory support is the selection of either air or "oxygen" can include other forms of ventilation to maintain oxygen saturation (Appendix 2).

These should be recorded at the same time points as the vital sign measurements (Table 1). NEWS2 values will be calculated electronically based on vital sign parameters and NEWS2 related assessments recorded by the investigator in the appropriate eCRFs.

In-hospital outcomes

In addition to the endpoints mentioned above, the following in-hospital outcomes will be captured on eCRF(s):

- Days on mechanical ventilation
- Days in hospital
- Days in ICU

- Days with use of supplemental oxygen
- Days on ECMO
- Time from intubation for mechanical ventilation to time to extubation

